### **5.4. Medical History**

All medical history will be coded using the Medical Dictionary for Regulatory Activities (MedDRA). The incidence of medical history abnormalities will be summarized using descriptive statistics by system organ class (SOC) and preferred term (PT). Patients are counted only once in each SOC category, and only once in each PT category.

### **5.5. Prior Therapy and Medication**

Any prior or concomitant medication, treatment, psychotherapy, or procedure a patient has had for migraine and/or depression within the past 10 years or for any indication within the past 5

months before IMP administration and up to the end of study, including follow-up, will be recorded on the eCRF. The sponsor will encode all therapy and medication according to the World Health Organization (WHO) drug dictionary (WHO Drug).

The incidence of prior therapies and medications will be summarized using descriptive statistics by therapeutic class and PT. Patients are counted only once in each therapeutic class category, and only once in each PT category. Prior therapies and medications will include all medications taken and therapies administered before the first day of study drug administration administration.

The subset of prior therapies and medications for migraine /headache will be summarized for the following categories:

- preventive medication from protocol appendix for migraine/headache
- opioids for migraine/headache
- NSAIDS for migraine/headache
- triptans for migraine/headache
- ergots for migraine/headache
- butalbital for migraine/headache
- medication from protocol appendix for other reason than depression
- benzodiazepines for other reason than anxiety/insomnia
- other

## **5.6. Electrocardiography**

ECG findings (normal, abnormal not clinically significant, and abnormal clinically significant) at baseline will be summarized using descriptive statistics.

## **5.7. Physical Examinations**

Patients with a physical examination, patients with at least 1 abnormal finding, and abnormal findings for each category at baseline will be summarized using descriptive statistics.

## **5.8. Childbearing Potential and Methods of Contraception**

For female patients, information related to childbearing potential and menopause will be collected at screening. Data will be listed.

## **5.9. Study Protocol Violations**

Data from patients with any important protocol deviations during the study will be summarized overall and for each category using descriptive statistics.

## 6. EFFICACY ANALYSIS

### 6.1. General

Migraine days will be defined as follows. If the headache fulfills the criteria for migraine on any given day, the consecutive days are part of the same migraine attack and are therefore considered to be migraine days as well (even if they do not fulfill the criteria for migraine). These days only reflect normal fluctuations in migraine severity that lead to or represent the resolution of a full-blown migraine attack. Accordingly, for the purpose of this study, a migraine day is endorsed when at least one of the following situations occurs:

- a calendar day (00:00 to 23:59) demonstrating at least 4 consecutive hours of a headache meeting the criteria for migraine with or without aura
- a calendar day (00:00 to 23:59) demonstrating at least 4 consecutive hours of a headache meeting the criteria for probable migraine, a migraine subtype where only 1 migraine criterion is missing
- a calendar day (00:00 to 23:59) demonstrating a headache of any duration that was treated with migraine-specific medications (triptans and ergot compounds)
- a calendar day (00:00 to 23:59) that is immediately consecutive (happening 1 day before or 1 day after) of any day fulfilling any of the 3 criteria above, where individuals report headache of any duration

The **monthly average number of days or hours** of efficacy variables (migraine days) **during the 12-week period** after the 1st dose of study drug will be derived and normalized to **28** days equivalent using the following formula.

$$\frac{\sum \text{Days or hours of efficacy variable over the 12 week period}}{\sum \text{Days with assessments recorded in the eDiary for the 12 week period}} \times 28 \quad (1)$$

The **monthly number of days or hours** of efficacy variables **during a 4-week period** after each dose will be derived and normalized to **28** days equivalent using the following formula, where monthly data separated by each visit of study drug dosing will be used.

$$\frac{\sum \text{Days or hours of efficacy variable during the 4 week period}}{\sum \text{Days with assessments recorded in the eDiary for the 4 week period}} \times 28 \quad (2)$$

The **baseline values** will be calculated using all data collected in the run-in period.

$$\frac{\sum \text{Days or hours of efficacy variable during the run – in period}}{\sum \text{Days with assessments recorded in the eDiary for the run – in period}} \times 28 \quad (3)$$

The **percentage of reduction** in the monthly average number of an efficacy variable will be calculated as

$$\frac{\text{baseline value} - \text{postbaseline value}}{\text{baseline value}} \times 100\% \quad (4)$$

where the baseline value is calculated by formula (3) and the postbaseline value in the equation is calculated by formula (1) for the variables *during the 12-week period* or by formula (2) for the variables *during the 4-week period* after each dose for months 1, 2, 3, and 6.

The mITT analysis sets will be used for all efficacy analyses. Summaries will be presented by treatment group as randomized, unless otherwise noted. For the double-blind treatment period, summaries will be presented by treatment group. For the open-label treatment period, summaries will be presented by double-blind treatment group and all patients (ie, total). Descriptive statistics for all efficacy data will be presented by month (or week), and over 12-week period for the double-blind period, and at month 6 (or week 24) for the open-label treatment period. For migraine days and PHQ-9 total score, months 1, 2, and 3 (or weeks 4, 8, and 12) will also be included in the open-label treatment period summaries.

The primary and secondary endpoints analysis listed in section 6.2.1 and section 6.3 will be repeated for the PP analysis set.

## 6.2. Primary Efficacy Endpoint and Analysis

### 6.2.1. Definition

The primary efficacy endpoint is the mean change in the monthly average number of migraine days from the 28-day baseline period during the 12-week period after the first dose of study drug.

### 6.2.2. Primary Efficacy Analysis

The hypothesis testing for the primary analysis is:

$$H_o : \delta_1 = \delta_2 \quad vs \quad H_a : \delta_1 \neq \delta_2$$

where  $\delta_1$  and  $\delta_2$  are the mean change from baseline in the monthly average number of migraine days for the fremanezumab treatment group and the placebo treatment group respectively.

The primary efficacy endpoint will be analyzed using an analysis of covariance (ANCOVA) model with sex, region (United States, European, or rest of world), migraine classification (ie, CM or EM), baseline PHQ-9 score category (10 to 14, 15 to 19, and  $\geq 20$ ), and treatment as factors and baseline number of migraine days as a covariate. The stratification factors (as randomized) will be used in the model. The least square (LS) mean treatment difference (fremanezumab - placebo), 95% confidence interval (CI) for the LS mean treatment difference, and the associated p-value will be generated from this model.

The statistical test will be two-sided at the alpha=0.05 level of significance. The SAS code for this test is as follows:

```
PROC MIXED;
  CLASS TREAT SEX REGION MIGCLASS PHQCAT;
  MODEL CHG= TREAT SEX REGION MIGCLASS PHQCAT BASE;
  LSMEANS TREAT / DIFF CL;
RUN;
```

The normality assumption for the ANCOVA model will be checked to ensure validity of the primary analysis. If the model assumptions are not met (p-value <0.01), a nonparametric method such as Wilcoxon Rank Sum test will be conducted as a sensitivity analysis.

### 6.2.3. Sensitivity Analysis

#### 6.2.3.1. MMRM Analysis

Sensitivity analysis will be performed using a mixed-effects model repeated measures (MMRM) analysis model to estimate the mean change from baseline in the monthly average of migraine days for the overall 3 months double-blind treatment period and by each month to support the primary analysis.

Each patient’s monthly number of migraine days during the 4-week period will be calculated by formula 2 in section 6.1. If a patient is early terminated or has intermittent missing days and has fewer than 10 days of electronic headache diary entries for a month, that month’s value will be considered as missing as described in section 4.3.

The MMRM model will include treatment, sex, region, migraine classification, baseline PHQ-9 score category, month, treatment-by-month interaction as fixed effects, baseline value as a covariate, and patient in the repeated statement as a random effect. The stratification factors (as randomized) will be used in the model. The unconstructed covariance structure will be used for the repeated observations within a patient. The LS mean treatment difference (fremanezumab - placebo), 95% CI for the LS mean treatment difference, and the associated p-value for fremanezumab versus placebo will be generated from this model for each month and overall 3 months.

The SAS code for this test is as follows:

```
PROC MIXED;
  CLASS USUBJID TREAT SEX REGION MIGCLASS PHQCAT MONTH;
  MODEL CHG= TREAT SEX REGION MIGCLASS PHQCAT BASE MONTH TREAT*MONTH;
  REPEATED MONTH / SUBJECT=USUBJID TYPE=UN;
  LSMEANS TREAT TREAT*MONTH / DIFF CL;
RUN;
```

This sensitivity analysis will be performed on the mITT analysis set.

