## **2.4. Sample Size and Power Considerations**

A sample size of 288 (144 per treatment group) evaluable patients completing the study will provide 90% power to detect a treatment difference of 2 days with a common standard deviation of 5.2 days in changes from the 28-day baseline period in monthly average migraine days between active and placebo groups at a 2-sided alpha level of 0.05. This sample size will provide approximately 80% power to detect a treatment difference of 2 points with a common standard deviation of 6 points in the change from randomization visit (day 1) in HAM-D 17 total score at a 2-sided alpha level of 0.05. Assuming a 15% drop-out rate, approximately 340 patients (approximately 170 patients per treatment group) will be randomized.

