#### **6.3.1.2. Analysis**

The HAM-D 17 total score change from baseline to week 8 will be analyzed using the same MMRM method as described in section 6.2.3.1. The analysis will also be done at weeks 4 and 12.

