#### **6.3.5.2. Analysis**

The HIT-6 disability score change from baseline to week 12 will be analyzed using the same MMRM method as described in section 6.2.3.1. The analysis will also be done at weeks 4 and 8.

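### The MMRM behind every continuous secondary endpoint fits one baseline slope to weeks 4, 8 and 12; adding baseline-by-month would cheaply protect precision and robustness if the slopes differ by visit

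*SAP*

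**What the plan says.** SAP 6.2.3.1 sets out the MMRM as a sensitivity analysis for migraine days. The fixed part contains treatment, the stratification factors, month, "treatment-by-month interaction as fixed effects, baseline value as a covariate, and patient in the repeated statement as a random effect". The code agrees: it has `BASE`, `MONTH` and `TREAT*MONTH` with an unstructured covariance, and no `BASE*MONTH`.

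The same model then becomes the analysis of the continuous secondary endpoints. For the key secondary, SAP 6.3.1.2 says: "The HAM-D 17 total score change from baseline to week 8 will be analyzed using the same MMRM method". For HIT-6, SAP 6.3.5.2 says: "The HIT-6 disability score change from baseline to week 12 will be analyzed using the same MMRM method". Sections 6.3.3.2 (MSQoL) and 6.3.4.2 (CGI-S) do likewise. Section 7 tests the secondary endpoints in a fixed sequence, so the week-8 and week-12 contrasts from this model carry confirmatory weight, as does CGI-S at week 4.

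For HAM-D 17, SAP 2.4 plans "approximately 80% power to detect a treatment difference of 2 points with a common standard deviation of 6 points". Neither document gives a baseline SD, a baseline-outcome correlation or an expected slope by visit for any of these scales.

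**The concern.** The model lets the treatment effect vary by month but holds the baseline effect constant. A day-1 score need not predict weeks 4, 8 and 12 equally well. Where it does not, the common slope is a weighted average that fits some visits better than others, and the misfit goes into the residual variance of the visits it fits less well. The tested contrasts are mostly at week 8 (HAM-D 17) and week 12 (MSQoL, HIT-6, the last CGI-S contrast), whereas the average can be dominated by week 4 if that visit is the least variable.

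Two things would then suffer: precision, and robustness to drop-out. With incomplete data the mean model partly stands in for unobserved week-8 and week-12 values, so a wrong slope matters more if drop-out depends on baseline.

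Other models in the plan do not impose this constraint. The primary ANCOVA (SAP 6.2.2) estimates a slope for its single outcome, and the imputation model in SAP 6.2.3.2 gives each month's regression its own baseline coefficient. No reason is given for equal slopes in the MMRM.

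**Working it through.** **1. The plan's own figures.** Inputs from SAP 2.4 and 6.2.2: 144 per arm, two-sided 0.05, HAM-D 17 difference 2 with SD 6, primary difference 2 with SD 5.2, 15% drop-out. Power = Φ(2/SE − 1.96), with SE = SD × √(2/144).
- HAM-D 17: SE = 0.707, 2/SE = 2.83, power 80.7% (stated: about 80%).
- Primary: SE = 0.613, 2/SE = 3.26, power 90.4% (stated: 90%).
- 288/0.85 = 339 (stated: about 340).

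All reproduce. The SD of 6 is an SD of change in a two-group comparison with no baseline adjustment.

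**2. Formula.** Let β_t be the true baseline slope at visit t, σ_B the baseline SD, and Σ the residual covariance given baseline, with SD σ_t at visit t. With complete data the common slope is b = (1′Σ⁻¹β)/(1′Σ⁻¹1). The variance of the visit-t contrast is
- one slope: (2/n)[σ_t² + (β_t − b)²σ_B²]
- with `BASE*MONTH`: (2/n)σ_t²

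The proportional increase is therefore (β_t − b)²σ_B²/σ_t², which is zero when the slopes are equal.

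**3. Assumed inputs (none from the documents).** σ_B = 5; residual SDs 4.2, 5.2 and 5.6 at weeks 4, 8 and 12; residual correlation 0.6. The weights in b are then 0.70, 0.21 and 0.09. Slopes are for the score itself; slopes for change are 1 lower, which leaves β_t − b unchanged.

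| Slopes wk 4/8/12 | b | Week 8 increase | Week 12 increase |
|---|---|---|---|
| 0.70/0.60/0.55 | 0.666 | 0.066² × 25/27.04 = 0.4% | 0.116² × 25/31.36 = 1.1% |
| 0.70/0.50/0.40 | 0.631 | 0.131² × 25/27.04 = 1.6% | 0.231² × 25/31.36 = 4.3% |
| 0.80/0.50/0.40 | 0.702 | 0.202² × 25/27.04 = 3.8% | 0.302² × 25/31.36 = 7.2% |

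A simulated MMRM (340 patients, 200 runs per row, about 10% drop-out related to the week-4 score) gave 0.6/1.1%, 1.9/4.2% and 4.3/7.6% for weeks 8/12.

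**4. HAM-D 17 power at week 8.** With the assumed residual SD of 5.2, power is 90.3%, 89.9% and 89.3% with one slope, against 90.4% with `BASE*MONTH`. If the week-8 residual SD is instead set so that the SD of change equals the stated 6, keeping b from the table, the pairs are 85.0/85.1%, 87.1/87.5% and 86.4/87.5%. Taking the largest simulated increase, 4.3%, gives 5.2 × √1.043 = 5.31 and power 89.2%, a loss of 1.2 points.

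**5. Wider inputs.** SD of change fixed at 6, baseline SD 4 to 6, residual correlation 0.5 to 0.7 between adjacent visits and lower between weeks 4 and 12. For change-score slopes −0.30/−0.45/−0.55 the week-8 increase is 0.02 to 1.2%, at most 0.4 power points. At baseline SD 5, power is 80.7% with no baseline term, 86.0 to 86.2% with the planned single slope and 86.2% with `BASE*MONTH`. A deliberately extreme set, −0.10/−0.45/−0.70, gives at most 6.4% and 2.0 points at week 8, and more than 10% at week 12 for some inputs.

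**6. Drop-out.** Simulation with 340 patients, roughly 15% drop-out, 1000 runs, true effect −2.00, change-score slopes −0.30/−0.45/−0.55. With random drop-out both models are unbiased; model SEs (single slope vs `BASE*MONTH`) are 0.619 vs 0.617 at week 8 and 0.676 vs 0.669 at week 12. In a stress test with drop-out driven by baseline in opposite directions by arm, the single-slope model gives −1.89 and −1.78 at weeks 8 and 12; with `BASE*MONTH` the estimates are −1.97 and −1.99.

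**The case against.** A common baseline slope with an unstructured covariance is a complete and reproducible specification. Baseline is adjusted for at every visit, and only the fineness of that adjustment is in question. The documents contain nothing to show that the slopes differ, and the week-12 percentages rest on assumed inputs, since MSQoL, CGI-S and HIT-6 have no stated SD, effect or power. The drop-out pattern that produced bias was chosen as a stress test, and no section of the protocol or SAP suggests it. All of this stands. It makes the point conditional and limits it to an improvement.

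A reader might also infer that the lost precision takes HAM-D 17 power below the planned 80%. The documents do not support that. Inflating the planning SD of 6 is the wrong calculation, because that SD carries no baseline adjustment, and the planned MMRM already adjusts for baseline. In every scenario above, the single-slope model has more power than the 80.7% reproduced from SAP 2.4. Nor do the documents support saying outright that the confirmatory contrasts are under-adjusted, or that type I error is at risk: with complete data or drop-out unrelated to baseline, the misfit is absorbed into the standard error.

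The objection does not supply a reason for the equal-slope constraint, or a material cost to removing it.

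**Conclusion.** The point holds as a conditional one. One baseline slope serves weeks 4, 8 and 12 for all the continuous secondary endpoints. If the true slopes differ by visit, the week-8 and week-12 contrasts lose some precision and some protection against drop-out related to baseline. Under the main assumed inputs the variance increase is about 0.4 to 4% at week 8, or roughly 0.1 to 1.2 power points for HAM-D 17, and about 1 to 8% at week 12. If the slopes are equal it is zero. These figures depend on an assumed baseline SD, residual SDs, residual correlation and slopes, and should be read as a range of possibilities. The primary ANCOVA, the stated sample size and the stated power are unaffected.

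**What to change.** Before unblinding, add `BASE*MONTH` to the MODEL statement of the MMRM in SAP 6.2.3.1, and say in the text that it applies to every endpoint analysed by that method with baseline as a covariate: HAM-D 17, MSQoL, CGI-S, HIT-6, HAM-A and WPAI. PHQ-9 needs no change, because SAP 6.4.1.2 leaves baseline out of its model. The treatment differences from the LSMEANS statement keep their meaning, since no treatment-by-baseline term is introduced.

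The cost is one model term and 2 degrees of freedom with about 340 patients. The timing matters: the same change made after unblinding would be a data-driven alteration of confirmatory analyses.

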#### 6.2.3.2. Analysis with Multiple Imputation Method

Sensitivity analysis will be performed by imputing missing migraine days of months 1-3 using MI method. The data will be processed by the following steps.

- If a patient has partial electronic headache diary data (ie, <28 days) for a month, that month’s value will be considered missing before the MI procedure.
- For the patients in the fremanezumab treatment group who are early terminated with reasons of adverse event (AE) or lack of efficacy, they will be assigned to placebo group so their missing values will be imputed using data from the placebo treated patients.
- Run SAS PROC MI procedure to create 100 complete datasets.

The following SAS code pertains to the MI analysis:

```
PROC MI DATA=XXX SEED=SEED OUT=MI_OUT NIMPUTE=100 MAXIMUM=. . . . . 28 28
28 MINIMUM=. . . . . 0 0 0;
  CLASS TREAT SEX REGION MIGCLASS PHQCAT;
  FCS REG (AVALMI1=TREAT SEX REGION MIGCLASS PHQCAT BASE/DETAILS)
  NBITER=100;
  FCS REG (AVALMI2=TREAT SEX REGION MIGCLASS PHQCAT BASE
  AVALMI1/DETAILS) NBITER=100;
  FCS REG (AVALMI3= TREAT SEX REGION MIGCLASS PHQCAT BASE AVALMI1
  AVALMI2/DETAILS) NBITER=100;
  VAR TREAT SEX REGION MIGCLASS PHQCAT BASE AVALMI1 AVALMI2 AVALMI3;
RUN;
```

- Within each imputed data set, for a patient who has partial, say  $X$  ( $X < 28$ ) days, electronic headache diary data in a month, the monthly value will be replaced by
- $\sum(\text{observed value}) + (28 - X) * \text{imputed value} / 28$
- The monthly average number of migraine days **during the 12-week double-blind period** after the 1st dose of study drug will be the average of month 1, month 2 and month 3 values.

Each dataset will be analyzed using the same ANCOVA model as described in section 6.2.2. The LS means and SEs from each analysis will be output to a SAS data set. The SAS code for this analysis is as follows:

```
ODS OUTPUT DIFFS=MIXED_OUT;
PROC MIXED DATA=UPDATED_MI_OUT METHOD=REML;
  BY _IMPUTATION_;
  CLASS TREAT SEX REGION MIGCLASS PHQCAT;
  MODEL CHG=TREAT SEX REGION MIGCLASS PHQCAT BASE;
  LSMEANS TREAT / DIFF CL;
RUN;
```

The output dataset from the above SAS code will contain the estimate of the LS mean treatment difference and the SE of the estimate from each of the 100 datasets. SAS procedure, PROC MIANALYZE, will be used to generate an overall LS mean treatment difference, 95% CI for the LS mean treatment difference, and associated p-value. The SAS code is as follows:

```
ODS OUTPUT PARAMETERESTIMATES=PARMEST;
PROC MIANALYZE DATA=MIXED_OUT ALPHA=0-.05 THETA0=0;
  BY TREAT;
  MODELEFFECTS ESTIMATE;
  STDERR=STDERR;
RUN;
```

This sensitivity analysis will be performed on the ITT analysis set.

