#### **3.1.4. Per-Protocol Analysis Set**

The PP analysis set is a subset of the mITT analysis set including only patients without important protocol deviations during the double-blind treatment period, including any deviation of the inclusion/exclusion criteria or any deviations or omissions of the IMP administration. Patients with less than 75% diary compliance during the double-blind treatment period will be excluded from the PP analysis set. A blinded data review meeting will be conducted prior to the database lock in order to determine the exclusion of the patients from the PP analysis set. After database lock and unblinding, patients who received study drug different from the study drug they were randomized to will also be excluded from the PP analysis set.

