### 4.3. Handling Withdrawals and Missing Data

If a patient has  $\geq 10$  days of electronic headache diary data after 1st dose of the study drug, his/her monthly average number of migraine days *during the 12-week period* or monthly number of migraine days *during the 4-week period* will be prorated to 28 days.

Multiple imputation (MI) method will be applied on the primary variable as sensitivity analyses. The methods will be described in detail in Section 6.2.3.

A patient's monthly number of migraine days *during the 4-week period* after each dose of study drug will be calculated for months 1, 2, 3, and 6. If a patient has missing diary days when calculating the monthly number of migraine days, the following method will be used to handle the missing data.

- If a patient has  $\geq 10$  days of electronic headache diary data for a month, the monthly number of migraine days will be prorated to 28 days for that month.
- If a patient has  $< 10$  days of electronic headache diary data for a month, the monthly number of migraine days will be considered as missing.

For the HAM-D, HAM-A and HIT-6, if 1 or more items are missing then the total score is missing. The missing questionnaire items handling for the MSQOL questionnaire is discussed in [Appendix E](#).

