### 4.4. Study Days and Visits

Study days are numbered relative to the 1st day of study drug administration. The start of treatment (day 1) is defined as the date on which a patient takes the 1st dose of study drug, as recorded on the study drug administration case report form (CRF). Days will be numbered relative to treatment start (ie, ..., -2, -1, 1, 2, ...; with day 1 being the 1st day of study drug administration and day -1 being the day before the 1st day of study drug administration).

The 4-week (28-day) visit windows for the electronic headache diary based efficacy endpoints will be determined based on the actual dosing day. The run-in phase is defined as day -28 to -1 before the 1st injection on day 1. Treatment phase including month 1, 2, 3, and 6 is from the beginning of the 1st injection of study drug to visit 6/day 169 or the EOT visit. The monthly visit windows are separated by each dosing date/time. Month 1 is from the date/time of the 1st dose of study drug administration on day 1 to the date/time just before the 2nd dose. Month 2 is from the date/time of the 2nd dose to the date/time just before the 3rd dose. Month 3 is from the date/time of the 3rd dose to the date/time just before the 4th dose. Month 6 is from 57 days after the date/time of the 4th dose to the EOT on day 169 approximately.

Throughout this document, all by month efficacy summaries for the headache data will refer to these visit windows.

For all other by-visit summaries, if there are multiple assessments at a postbaseline visit then the last non-missing assessment at that visit will be used for the summary. This includes assessments at the scheduled and unscheduled visits.

For patients who withdraw from the study, their efficacy and safety data at the early termination visit will be excluded from the by-visit summaries but will be included in the last assessment summaries.

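### The multiple-imputation sensitivity analysis blanks every month with fewer than 28 diary days before PROC MI, so neither a leaver's last month nor a stayer's near-complete month informs the imputation

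*SAP*

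**What the plan says.** SAP 6.2.3.2 works in a fixed order.

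1. A step that opens "If a patient has partial electronic headache diary data (ie, <28 days) for a month" declares the month missing before imputation.
2. Fremanezumab patients who stop early for an adverse event or lack of efficacy are moved to the placebo group for imputation.
3. PROC MI imputes month 1 from treatment, the stratification factors and baseline; month 2 from those plus month 1; month 3 from those plus months 1 and 2. The statement reads "VAR TREAT SEX REGION MIGCLASS PHQCAT BASE AVALMI1 AVALMI2 AVALMI3".
4. Only then, where a patient has X (<28) days of "electronic headache diary data in a month, the monthly value will be replaced by" the observed sum plus (28 − X) × imputed value / 28.

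No later step re-imputes anything. On population, "This sensitivity analysis will be performed on the ITT analysis set"; SAP 6.1 uses the mITT sets for efficacy generally.

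Elsewhere the plan treats partial months differently. In SAP 4.3, with at least 10 days, "the monthly number of migraine days will be prorated to 28 days for that month". The MMRM (SAP 6.2.3.1) drops a month only when a patient "has fewer than 10 days of electronic headache diary entries for a month". On month length, SAP 4.4 says: "The monthly visit windows are separated by each dosing date/time". Protocol Table 4 allows ±3 days at days 29, 57 and 85. The plan's own compliance limit is in SAP 3.1.4: "Patients with less than 75% diary compliance during the double-blind treatment period will be excluded from the PP analysis set".

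**The concern.** The rule has no tolerance for one missed entry, and the add-back comes too late to help any other month. When a leaver's month 3 is imputed, a random draw stands where the observed part of month 2 should be. A stayer with 27 of 28 days in a month contributes nothing from that month to the fitted regressions.

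Read literally, the rule also catches a dose-to-dose month of, say, 26 days in which every day was recorded. The add-back would then add imputed days beyond the month's actual end.

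The analysis exists to show how far the primary result depends on its missing-data assumption. If it differs from the primary result, part of the gap may come from the 28-day cutoff and not from the assumption under test.

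**Working it through.** **Planned scale (SAP 2.4).** Difference 2, SD 5.2, 144 per arm: SE = 5.2 × √(2/144) = 0.613; power = Φ(2/0.613 − 1.96) = 0.904, against 90% stated. Randomized: 288/0.85 = 339, against about 340. With 170 per arm, SE = 5.2 × √(2/170) = 0.564, the yardstick below.

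**One patient through the rules.** Month 1 has 27 of 28 days; the patient leaves after 14 days of month 2.
- MMRM: both months have at least 10 days, so both enter.
- Imputation model: 27 < 28 and 14 < 28, so none of the 41 recorded days enters.
- After add-back: month 1 is the observed sum + imputed/28; month 2 is the observed sum + 14 × imputed/28; month 3 is wholly imputed, conditional on two draws.

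**How strict the cutoff is.** One missed day in each of three 28-day months gives 81/84 = 96.4%, against a 75% limit of 63/84. That patient gives the MMRM three months and the imputation model none. If days are completed independently (an assumption), a 28-day month is complete with probability 0.98^28 = 0.568 or 0.95^28 = 0.238. With clustered misses (beta-binomial, ICC 0.1 / 0.3) the values are 0.768 / 0.878 at 98% completion and 0.514 / 0.721 at 95%.

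**Month length.** Month 1 can run 25 to 31 days, and months 2 and 3 can run 22 to 34. If every visit is uniform on −3 to +3 days, 43% of months are shorter than 28 days; if half the visits are on target and half uniform, 29%.

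**Effect on the treatment difference (simulation, assumed inputs).** From the documents: 340 patients, 15% leaving, SD 5.2, difference about 2. Assumed: leaving on a random day before day 84, either at random or after a poor month 1; residual month correlation 0.5 or 0.7; completion 100%, 98% or 95%; all or half of active leavers imputed from placebo; skips unrelated to migraine. There were 112 scenarios × 200 runs with 10 imputations (the SAP plans 100), 0–28 bounds and the printed predictor lists; Monte Carlo SE was at most 0.009. The reference is the same placebo-based imputation with a complete diary up to withdrawal, 28-day months, the partial month (≥10 days) as predictor, and add-back for the termination month.

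| Diary | Visits | Shift toward zero, days |
|---|---|---|
| perfect | on target | 0.011 to 0.040 |
| 98%, clustered misses | on target | 0.023 to 0.072 |
| 95%, clustered misses | on target | 0.045 to 0.088 |
| independent misses | on target | 0.032 to 0.131 |
| perfect | half off | 0.022 to 0.080 |
| clustered misses | half off | 0.032 to 0.117 |
| independent misses | half off | 0.039 to 0.145 |

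- Largest value on this grid: 0.145/0.564 = 0.26 SE. Perfect diary, on target: at most 0.040/0.564 = 0.07 SE.
- Moving from the reference to the primary ANCOVA, the missing-data assumption alone, shifts the difference by 0.04 to 0.12 days. The cutoff effect reached that size in 0 of 8 scenarios (perfect, on target), 6 of 32 (clustered, on target) and 31 of 72 (the rest).
- Leavers' mean change is off by −0.27 to −1.44 days when poor responders leave (they look better than their diaries) and by +0.05 to +0.34 when leaving is random.
- Against the ≥10-day threshold, the SAP rule's SE is 0 to 10% smaller and the test statistic changes by −0.07 to +0.13.

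**Outside that grid.** A smaller simulation (150 runs, no placebo reassignment, leaving driven by poor days in the partial month) gave −1.82 against −1.88 at 15.5% dropout, a shift of 0.06, and −1.66 against −1.86 at 24% dropout, a shift of 0.20. Making skips likelier on migraine days gave shifts of about 0.2 to 0.3 days, or 0.2/0.564 = 0.35 to 0.3/0.564 = 0.53 SE.

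**After changing only the threshold to ≥10 days.** The difference came within about 0.02 days of the reference in all 112 scenarios, and within about 0.03 to 0.10 days when skips depend on migraine, still closer than the SAP rule.

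**The case against.** A reader might infer that the observed days are thrown away. They are not: the add-back keeps them in their own month, and for a 27-of-28-day month the imputed part is only 1/28 of a drawn value. Earlier months with 28 or more entries also still inform later ones. What is lost is the information carried to other months and to the model fit.

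A reader might also infer that the primary result is compromised or that fremanezumab is favoured. The documents do not support this. The primary ANCOVA and the MMRM use other rules, and in the scenarios the estimate moves toward zero.

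It is also tempting to treat 0.26 SE as a ceiling, or the problem as one of early leavers only. The first is the maximum of one grid. On the second, the largest shifts on that grid come from near-complete months of patients who stay, or from off-target visits. The documents fix neither diary completion nor visit spread, and protocol 6.1.1 allows missed entries to be caught up within 48 hours, so near-perfect diaries are possible.

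Other objections stand in part:
- The 75% limit governs the per-protocol set and site monitoring, not imputation inputs; it only shows how strict 28 of 28 is.
- A fully recorded 26-day month is arguably not partial, since SAP 4.4 also describes the windows as four weeks. This calls for clarification.
- The analysis already differs from the primary in set (ITT against mITT) and weighting (mean of three months against pooled days), so a gap was never a pure test of the missing-data assumption. The cutoff adds one more avoidable difference.

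**Conclusion.** The concern holds for one sensitivity analysis. The mechanism follows directly from the order of steps in SAP 6.2.3.2 and is inconsistent with the 10-day rule in SAP 4.3 and 6.2.3.1. It deserves correction because, under the SAP, this is the only ITT and the only placebo-based analysis of the primary endpoint.

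The size is less certain than the mechanism. At the planned 15% dropout, with skips unrelated to migraine, the shift is about 0.01 to 0.04 days with perfect diaries and on-target visits, and up to about 0.14 days with incomplete diaries or off-target visits. Higher dropout or migraine-related skipping can take it to about 0.2 to 0.3 days. These are scenario values, not bounds; beyond the planned dropout, the documents do not supply the inputs.

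**What to change.** In SAP 6.2.3.2:

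1. Before PROC MI, set a month to missing only if it has fewer than 10 diary days. Otherwise enter its formula (2) value, both as outcome and as predictor.
2. State that a dose-to-dose month with every day recorded is complete, whatever its length.
3. Separately, check the MAXIMUM and MINIMUM lists. As printed, each has eight entries (five dots, three numbers) for nine VAR variables; read by position, the 0–28 limits fall on BASE, AVALMI1 and AVALMI2. Nine entries are needed for them to fall on AVALMI1 to AVALMI3. If an entry was lost in conversion from PDF, confirming this is enough. The main point does not depend on it.

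The cost is SAP wording and a little code, with no new data and no second PROC MI run. The downside is that months with 10 to 27 days carry the proration assumption of the primary analysis, so their skipped days are prorated and no longer imputed. That is weakest when skipping depends on migraine.

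For termination months the add-back formula may be kept, so that placebo-based imputation still covers the unobserved days. That option needs an imputed value for the month; prorating it instead costs about 0.02 days at most in the scenarios above.
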